## All SAEs will be:

- Reviewed and evaluated by a study clinician
- Recorded on the appropriate Adverse Event CRF
- Followed through resolution by a study clinician
- A study clinician will determine whether the SAE is considered related to study treatment.

# 9.2.4. Procedures to be Followed in the Event of Abnormal Laboratory Test Values or Abnormal Clinical Findings

Collection of specific safety laboratory data is outlined in the study visit schedule. Toxicity tables are based on the FDA toxicity tables developed for normal healthy adult volunteers.

Laboratory values that are abnormal based on the toxicity tables will be reported on the appropriate CRF.

In the event a subject experiences an AE or vulvar or vaginal reaction that is still present at the end of the subject's participation in the study, the subject must be followed until resolution of the event or until the event or abnormality stabilizes to the investigator's and/or sponsor's satisfaction. Follow-up procedures, evaluations, and outcomes will be recorded on the subject's CRFs.

## 9.3. Reporting Procedures

#### 9.3.1. Adverse Events

AEs including local and systemic reactions not meeting the criteria for SAEs will be captured on the appropriate CRF. Solicited AEs will be collected from the time of the first product administration through Day 5. Non-solicited AEs and SAEs will be collected from the time of first product administration throughout the entire study period. Information to be collected includes event description, date of onset, investigator assessment of severity, investigator assessment of relationship to study product, date of resolution of the event, seriousness, and outcome. The intensity of non-serious AEs will be assessed by a licensed study clinician (i.e., medical doctor, nurse, nurse practitioner, physician's assistant). The causality of non-serious AEs will be assessed by a licensed clinician able to make diagnoses listed on the Form FDA 1572. All AEs occurring during the AE reporting period of the study will be documented appropriately regardless of relationship. All AEs will be followed to adequate resolution or until considered stable.

Any medical condition that is present at the time of enrollment will be considered as pre-existing at Baseline and will not be reported as an AE. If the severity or frequency of any pre-existing medical condition increases during the study period, then it will be recorded as an AE.

AEs will be followed until resolution even if this extends beyond the study-reporting period. Resolution of an AE is defined as the return to pretreatment status or stabilization of the condition with the expectation that it will remain chronic.

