# 3.2. Study Outcome Measures

# 3.2.1. Safety Outcomes

All safety outcomes will be assessed in the safety analysis population of all subjects who received one or more doses of study product. Outcomes will be reported by treatment arm.

- Primary Safety Outcome
  - Number of subjects reporting solicited urogenital AEs following the first dose of the study product through Visit 2 (Day 8-15).
  - Number of subjects reporting serious adverse events (SAEs) considered product-related following the first dose of the study product through Visit 3 (Day 22-31)
- Secondary Safety Outcomes
  - Number of subjects experiencing non-laboratory non-solicited AEs following the first dose of the study product through Visit 3 (Day 22-31).

• Number of subjects experiencing laboratory AEs following the first dose of the study product through Visit 2 (Day 8-15).

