#### 9.2.2. Solicited Events

Solicited events assessments will be captured on a memory aid starting on Day 1, the first day of therapy and continuing for 5 days.

The subject will record the presence and intensity of vulvo-vaginal solicited events on the memory aid.

**Table 2:** Solicited events & grading

	Grade 1 Mild	Grade 2 Moderate	Grade 3 Severe	
Vaginal odor	Mild unpleasant odor	Moderate unpleasant odor	Severe, unpleasant odor	
Vaginal pain	Pain causing no or minimal interference with usual social and functional activities  Pain causing greater than minimal interference with usual social and functional activities or the need for non-narcotic medication		Pain causing inability to perform usual social and functional activities or the need for narcotic medication	
Vaginal tenderness	Mild tenderness	Moderate tenderness	Severe tenderness	
Vulvar/vaginal itching	Itching causing no interference with usual social and functional activities	Itching causing interference with usual social and functional activities	Itching causing inability to perform usual social and functional activities	
Vaginal dryness	Dryness not interfering with sexual function, social, and functional activities	Dryness causing greater than minimal interference with usual sexual, social and functional activities	NA	
Vaginal discharge by participant's report	Mild increase in participant's usual amount of discharge, regardless of color or quantity; no sanitary protection required	Moderate to profuse increase in discharge requiring pad use or other hygienic intervention	NA	
Vulvar inflammation (Redness/Swelling)	Mild swelling, or redness; no interference with usual, social and functional activities	Moderate swelling, or redness; interference with usual, social and functional activities	Severe swelling or redness, or presence of mucosal ulceration; inability to perform usual, social and functional activities	

Any symptoms still present on Day 5 will continue to be followed by subject memory aid notations until symptom resolution. Subjects will also be asked to record any medications taken and any emergency room or physician visits (other than routine check-ups).

Severity of solicited events symptoms are graded according to the table above. For symptoms not specifically mentioned will be graded using the following scale:

- Grade 1: Mild (does not interfere with activity)
- Grade 2: Moderate (interferes with activity)
- Grade 3: Severe (prevents daily activity)

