## 11.7.1. Safety Analyses

## 11.7.1.1. Overview of Safety Analyses

#### Solicited Adverse Event Data

Descriptive techniques will be used to summarize the solicited adverse events data. Local and systemic solicited events will be tabulated, with symptom type crossed by severity grade.

Tables will be prepared for each treatment arm, and for the combined safety analysis cohort. The data in each table will also be depicted graphically, as a bar-chart of symptom incidence, and provided as listings of events. In the tables, figures and listings, color-coding using a heat chart (yellow, orange, red) will be used to highlight severity (mild, moderate, severe).

The solicited AE outcome data consist of multiple symptoms types, with ordinal severity grades, taken repeatedly over a 5-day reporting period following first administration of study product. To facilitate analysis and interpretation, the data will be simplified in different ways in different analyses. For example, individual symptoms will be used to form the composite endpoint "any local symptom". The ordinal severity grades will be dichotomized, *e.g.*, none or mild versus moderate or severe. The grade will be summarized by the maximum severity over the five day reporting period so as to obtain a single observation per subject.

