9.3.1. Solicited Events and Symptoms

Solicited urogenital symptoms were collected before study product administration, and then daily for 5 days and graded on a scale of 0 (absent), 1 (mild), 2 (moderate) and 3 (severe). Urogenital symptoms include: vaginal odor, vaginal pain, vaginal tenderness, vulvar/vaginal itching, vaginal dryness, vaginal discharge, and vulvar inflammation. Any symptom that is present at the time that the subject is screened should be considered as baseline and not reported as a solicited urogenital AE. However, if it deteriorates at any time during the study, it will be recorded as a solicited urogenital AE. If a symptom is reported that was not present at baseline, it too will be recorded as a solicited urogenital AE. Treatment emergent solicited urogenital adverse events will be identified by comparing the severity of the baseline solicited urogenital symptoms with the severity of the post-baseline solicited urogenital symptoms. If the severity increases post-baseline or the symptoms appears post-baseline when it was 'None' at baseline, then the symptom will be considered to be treatment-emergent.

The first primary safety endpoint is the number of subjects reporting treatment-emergent solicited urogenital AEs following the first dose of the study product through Visit 2 (Day 8-15).

The number and percent of subjects reporting at least one treatment-emergent solicited urogenital adverse event will be summarized for each solicited adverse event and any solicited adverse event along with the 95% Clopper-Pearson CI and presented in **Table 62**. **Table 63** will present the proportion of subjects experiencing any solicited urogenital event and each specific urogential solicited event, along with the 95% Clopper-Pearson CI of the proportion, the difference in the proportions of subjects experiencing a solicited event between 5% Monolaurin Vaginal Gel and Placebo Gel, the 95% Exact CI of the difference and the p-value for a Fisher's exact test. A Fisher's exact test will be performed to test for the difference in the proportion of subjects reporting a treatment emergent solicited urogenital adverse event. The null hypothesis is that there is no difference in proportions of subjects reporting solicited urogenital AEs between treatment groups, with a two-sided alternative which considers the possibility of a difference in either direction. Section 6.1 provides pseudo SAS code to use for the analyses.

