For each treatment-emergent solicited urogenital adverse event and any solicited adverse events, the maximum severity over 5 days after the first dose will be summarized for the Safety population. The number and percentage of subjects reporting each treatment-emergent solicited adverse event will be summarized by the maximum severity and actual treatment group along with the 95% Clopper-Pearson CIs. For each event the denominator is the number of subjects with non-missing data for the specific solicited urogenital adverse event. See **Table 64** and **Figure 6**.

Table 64 and **Figure 7** will summarize any reported solicited symptom (treatment-emergent and non treatment-emergent) and each solicited symptom by maximum severity over 5 days after the first dose along with the 95% Clopper-Pearson CI for the Safety population. The number and percentage of subjects reporting each symptom will be summarized by the maximum severity and actual treatment group. For each event, the denominator is the number of subjects with non-missing data for the specific symptom. Maximum severity of solicited symptoms is displayed by study day and treatment group in **Figure 8**.

The number of subjects reporting a solicited symptom will be summarized for each day for all subjects and separately for each treatment group (**Tables 66-68**) and graphically in a bar chart (**Figure 7**).

Solicited symptoms by subject will be presented in Listing 12.

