Table 64 Number and Percentage of Subjects Experiencing Treatment Emergent Solicited Urogenital Adverse Events by Symptom, Maximum Severity, and Treatment Group- Safety Population (continued)

Notes: Denominator for percentages is the number of subjects in the Safety Population (N) with treatment emergent solicited urogenital adverse event data available for the specific solicited urogenital adverse event for each treatment group.

¹Each subject's maximum severity is reported for each treatment emergent solicited urogenital adverse event across all doses. Table includes solicited urogenital adverse events reported from the first dose of study product through Visit 2.

Solicited Symptom	Severity	5%	Monolaurin V (N=X)	Vaginal Gel		Placebo (N=X)	Gel)	All Subjects (N=X)				
	· ·	n	%	95% CI	n	%	95% CI	n	%	95% CI		
	None	x	х	x,x	x	х	X,X	х	х	X,X		
	Mild	x	х	X,X	x	х	X,X	х	х	X,X		
	Moderate	x	х	x,x	x	х	x,x	х	х	X,X		
Any Solicited Symptom	Severe	x	х	X,X	x	х	X,X	х	х	X,X		
	Not Reported	x	х	X,X	x	х	X,X	х	х	X,X		
	Total	х	х	x,x	х	х	x,x	х	х	X,X		
	None	x	х	X,X	х	х	X,X	х	х	X,X		
	Mild	х	х	x,x	х	х	x,x	х	х	X,X		
VerinelOlen	Moderate	х	х	x,x	х	х	x,x	х	х	X,X		
Vaginal Odor	Severe	х	х	X,X	х	х	X,X	х	х	X,X		
	Not Reported	х	х	x,x	х	х	X,X	х	х	X,X		
	Total	х	х	X,X	х	х	X,X	х	х	X,X		
	None	х	х	x,x	х	х	x,x	х	х	X,X		
	Mild	х	х	X,X	х	х	X,X	х	х	X,X		
Versional Daire	Moderate	x	х	X,X	х	х	X,X	х	х	X,X		
Vaginal Pain	Severe	x	х	x,x	x	х	x,x	х	х	X,X		
	Not Reported	x	х	x,x	x	х	x,x	х	х	X,X		
	Total	х	х	x,x	х	х	x,x	х	х	X,X		
	None	x	х	x,x	x	х	x,x	х	х	X,X		
	Mild	x	х	x,x	x	х	x,x	х	х	X,X		
Verinel Tendemoore	Moderate	х	х	X,X	х	х	X,X	х	х	X,X		
vaginai i enderness	Severe	x	X	X,X	x	X	X,X	X	x	X,X		
	Not Reported	x	х	X,X	x	x	X,X	х	х	X,X		
	Total	х	х	X,X	х	х	X,X	х	х	X,X		

Table 65:Number and Percentage of Subjects Experiencing Solicited Symptoms by Symptom, Maximum Severity, and
Treatment Group - Safety Population

Solicited Symptom	Severity	5%	Monolaurin (N=X)	Vaginal Gel		Placebo (N=X	Gel)	All Subjects (N=X)			
	·	n	%	95% CI	n	%	95% CI	n	%	95% CI	
	None	х	х	x,x	х	x	x,x	х	х	X,X	
	Mild	х	х	x,x	х	x	x,x	х	х	X,X	
x7 1 /x7 · 1 x/ 1 ·	Moderate	х	х	x,x	х	x	x,x	х	х	X,X	
Vulvar/Vaginal Itching	Severe	х	х	X,X	х	x	x,x	x	х	X,X	
	Not Reported	х	х	X,X	х	x	x,x	х	х	X,X	
	Total	х	х	X,X	х	x	x,x	х	х	X,X	
	None	х	х	X,X	х	x	x,x	х	х	X,X	
	Mild	х	х	X,X	х	x	x,x	х	х	X,X	
Vaginal Dryness	Moderate	х	х	X,X	х	х	x,x	х	х	X,X	
v aginar Dryness	Not Reported	х	х	X,X	х	х	x,x	х	х	X,X	
	Total	х	х	X,X	х	x	x,x	х	х	X,X	

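### The first primary safety outcome runs through Visit 2, but new solicited symptoms are collected only through Day 5, and the plan contradicts itself on whether later onsets count

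*Protocol*

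**What the plan says.** Protocol 3.2.1 gives the first primary safety outcome as "Number of subjects reporting solicited urogenital AEs following the first dose of the study product through Visit 2 (Day 8-15"). Protocol 11.3, 11.4 and 11.7.1.2 and SAP 3.2.4 use the same window. SAP 9.3.1 narrows the outcome to treatment-emergent events and keeps the window through Visit 2: "The first primary safety endpoint is the number of subjects reporting treatment-emergent solicited urogenital AEs following the first dose of the study product". Protocol 11.4 makes it one of three formal hypothesis tests, and Table 63, which carries the p-value, is titled through the Test of Cure visit.

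The collection rules are shorter. Protocol 9.3.1 states: "Solicited AEs will be collected from the time of the first product administration through Day 5". Protocol 9.2.2 states: "Solicited events assessments will be captured on a memory aid starting on Day 1, the first day of therapy and continuing for 5 days". It makes one exception: "Any symptoms still present on Day 5 will continue to be followed by subject memory aid notations until symptom resolution". Protocol 11.7.1.1 describes the analysis data as "taken repeatedly over a 5-day reporting period following first administration of study product".

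The SAP differs within itself. For the severity summary its Section 9.3.1 says that "the maximum severity over 5 days after the first dose will be summarized for the Safety population". The Table 64 footnote says: "Table includes solicited urogenital adverse events reported from the first dose of study product through Visit 2". Table 65 has a matching footnote.

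**The concern.** The window is part of the definition of a primary outcome. Here the definition reaches Visit 2, while the instrument stops asking about new symptoms at Day 5. A report that follows the Table 63 title would present a proportion, a difference and a p-value as covering the period through Visit 2, although new onsets were solicited for only part of it. A programmer who builds Tables 63 to 65 has two instructions that cannot both be met.

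The period in doubt is of interest for this product. The plan gives the last dose on Day 3, or on Day 4 for a subject first dosed after 3 pm (implementation note to SAP Listing 9). Solicitation of new symptoms thus ends one or two days after the last planned dose. The protocol's rationale names prevention of vaginal candidiasis as a potential advantage, and symptoms of that kind could appear after the course has ended.

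**Working it through.** No power, sample-size or alpha figure in either document depends on this window, so there is no figure of the plan to reproduce. The check is a comparison of passages with some day arithmetic.

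**Step 1. Windows side by side.**
- Outcome definition (Protocol 3.2.1, 11.3, 11.4, 11.7.1.2; SAP 3.2.4, 9.3.1) and Table 63 title: first dose through Visit 2.
- Collection (Protocol 9.2.2, 9.3.1; SAP 4.5, 9.3.1): Days 1 to 5, with longer follow-up only for symptoms present on Day 5.
- Severity text in SAP 9.3.1 for both summaries, treatment-emergent events and all symptoms: 5 days. The SAP text cites Table 64 for both, but the content of the second is that of Table 65.
- Footnotes of Tables 64 and 65: through Visit 2.
- Daily tables 66 to 68: columns for Pre-Dose and Days 1 to 5 only.
- Table 62: no window stated.

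**Step 2. Follow a symptom through the rules.**
- New or worse by Day 5, whether or not it persists: counted under every reading. SAP 9.3 counts each subject once per event, so longer follow-up adds nothing to the count.
- Present at baseline, unchanged through Day 5, worse later: still followed on the memory aid. It counts under the Table 64 footnote but not under the 5-day text.
- First onset between Day 6 and Visit 2: no solicited entry is planned. Listing 12 adds rows after Day 5 only for ongoing symptoms. SAP 9.3.1 says, with no day limit, that a symptom absent at baseline is recorded as a solicited event, but it does not say from which record a late one would be taken. If handled as unsolicited, it goes to the secondary outcome in Table 69, which gives a difference and exact confidence interval but no p-value.

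The any-event comparison can therefore change only through subjects with no treatment-emergent solicited event by Day 5 whose first one comes later.

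**Step 3. Days concerned.** With Visit 2 on day V, the part of the defined window without solicitation of new onsets is (V − 5)/V.
- V = 8: (8 − 5)/8 = 3/8 = 38% (Days 6 to 8).
- V = 15: (15 − 5)/15 = 10/15 = 67% (Days 6 to 15).

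These are shares of calendar days, not of events. The documents give no rate of late onset, so neither the number of subjects affected nor the effect on the between-arm difference can be computed.

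**Step 4. Look for a rule that closes the gap.** Protocol 8.1 has study personnel take a history of largely the same symptoms, Protocol 7.2 reviews symptoms and adverse events at Visit 2, and Listing 11 holds graded clinical assessments at Visits 1, 2 and 3. No section of either document derives the primary safety outcome from any of these.

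**The case against.** The strongest reply is that SAP 9.3.1 already includes late events. It records as solicited any baseline symptom that deteriorates and any symptom not present at baseline, and neither sentence stops at Day 5. Its treatment-emergent rule compares baseline with post-baseline severity, also without a limit. The history in Protocol 8.1 could supply the data, and the Table 64 footnote could describe reports gathered up to Visit 2. This stands in part. A reader might infer from Protocol 9.3.1 that onsets from Day 6 are excluded from the primary outcome, but no passage states such an exclusion, and the SAP sentences point the other way. They do not settle the matter either, because they name no source for late onsets and Protocol 9.3.1 gives Day 5 explicitly.

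Three further points stand. Late onsets treated as unsolicited are not lost: Table 69 compares them between arms, Tables 77 to 82 split events at Visit 2, and fungal overgrowth is examined separately by KOH mount and culture at Visits 2 and 3. The collection rule is the same in both masked arms, so the Fisher test remains valid for what is collected. The 5-day reporting period is stated openly in Protocol 11.7.1.1, and a 5-day window may be a reasonable choice in itself. None of these reconciles the stated window with the one collected.

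**Conclusion.** The inconsistency is real and should be corrected. The first primary safety outcome and its test are said to run through Visit 2, new symptoms are solicited only through Day 5, and the SAP text and table footnotes disagree. The status of a symptom that starts between Day 6 and Visit 2 is contradictory, and no derivation rule brings it in. The period in doubt is 3 to 10 days, or 38% to 67% of the defined window. This assumes a Visit 2 within Days 8 to 15 and use of the memory aid as Protocol 9.2.2 describes.

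Two stronger readings are not supported. The documents do not show that late symptoms are excluded by rule, only that the rules conflict. They also do not show that the safety comparison is biased or that events go unrecorded. What needs correcting is the statement of what the primary proportion and p-value cover.

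**What to change.** Before database lock and unblinding:

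1. Restate the outcome as onset or worsening from first dose through Day 5, with symptoms ongoing at Day 5 followed to resolution. The places are Protocol 3.2.1, 11.3, 11.4 and 11.7.1.2, SAP 3.2.4 and 9.3.1, the Table 63 title and the footnotes of Tables 64 and 65. If the protocol is not amended, record the change in SAP Section 12, where the SAP already explains its departure on LOCF.
2. Bring the SAP 9.3.1 sentences that have no day limit into line, and say explicitly that a worsening after Day 5 of a symptom already under follow-up is listed but not counted in the primary outcome.
3. As a supplementary analysis only, count by arm the subjects with any of the seven symptoms starting after Day 5 and up to Visit 2, from the unsolicited adverse event records. Note that late odor and discharge may reflect unresolved bacterial vaginosis.

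Adding the clinician's Visit 2 grades from Listing 11 to the primary outcome is not advised. It would mix clinician grading with self-report and could count treatment failure as intolerance.

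The cost is changes of wording and one extra table from data already planned. No new collection is needed, and the test is unchanged.

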#### 9.3.1.1. Serious Adverse Events

Information to be collected includes event description, date of onset, investigator assessment of severity, investigator assessment of relationship to study product, date of resolution of the event, seriousness, and outcome. The intensity of SAEs will be assessed by a licensed study physician. The causality of SAEs will be assessed by a licensed physician able to make diagnoses listed on the Form FDA 1572.

Serious adverse events will be recorded on the appropriate Adverse Event CRF and will be reported to the site's Independent Safety Monitor. Events will be reviewed and followed to resolution by a study physician. SAEs will be collected on each subject until her last study visit.

Any AE that meets a protocol-defined serious criterion must be submitted immediately (within 24 hours of site awareness) on an SAE form to the DMID Pharmacovigilance Group, at the following address:

DMID Pharmacovigilance Group Clinical Research Operations and Management Support (CROMS) [name] SAE Hot Line: [name] (US) or [name] (outside US)

SAE Hot Line: [name] (US) or [name] (outside US)
SAE FAX [contact] (US) or [name] (outside US)

**SAE Email Address:** [contact]

Additionally, materials must be submitted to the Statistical and Data Coordinating Center (SDCC), Emmes Corporation, through the IDES system. Other supporting documentation of the event may be requested by the DMID Pharmacovigilance Group and should be provided as soon as possible.

The DMID Medical Monitor and Clinical Protocol Manager will be notified of the SAE by the DMID Pharmacovigilance Group. The DMID Medical Monitor will review and assess the SAE for regulatory reporting and potential impact on study subject safety and protocol conduct.

At any time after completion of the study, if the investigator becomes aware of an SAE that is suspected to be related to study product, the investigator will report the event to the DMID Pharmacovigilance Group.

